# 3.8 Study Endpoints

# 3.8.1 Primary end-point

Treatment engagement is the primary endpoint in this study.

- Confirmation of enrollment in MAT: Assessments will collect self-report of participation in MAT at the time
  of assessment as well as during the intervening time-period. We will also collect confirmatory
  documentation from the identified treatment provider. Permission to contact the treatment provider will be
  included in the consent and a specific release of information form signed by the participant will be included
  in the request for confirmation.
- CARES Integrated Data Systems Service Utilization: Participants enrolled in this study will provide consent to allow the Health Department to review their records of utilization of city services prior to and following enrollment in the study.

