#### 3.4 Study Objectives

The proposed research will evaluate the ability of a mobile, rapid induction procedure to engage individuals in ongoing medication assisted treatment. Individuals meeting criteria for opioid use disorder and at high risk of opioid overdose will be enrolled in the study. Recruitment will take place in two targeted neighborhoods with a high prevalence of fatal and non-fatal opioid overdose. A total of 250 participants will be engaged in the research at the time they seek treatment. Following informed consent and determination of eligibility, 125 individuals will be enrolled as they engage with the mobile, rapid induction team and 125 individuals will be enrolled as they seek treatment from the BAC/CRC. All participants will be assessed at 1- and 6-month following enrollment. These assessments will provide data able to address each of the three aims.

- **Aim 1:** To evaluate the impact of the mobile, transitional MAT intervention on its ability to engage participants in targeted, existing MAT treatment slots at 1- and 6-month post-enrollment.
- Aim 2: To evaluate the impact of the mobile intervention on subsequent drug use and overdoses at 6-month postenrollment.
- Aim 3: To assess the acceptability and costs of the intervention. We will document the program and patient costs of delivering and participating in the intervention.

Assessments will also provide data on factors that are considered to be important determinants of retention in treatment—duration of opioid use; prior number of treatment attempts; frequency of recent use; and, depression. In addition to age, gender, and race these variables will be used in the proposed propensity analyses.

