# 4.8.3 Screening assessments

For those who remain interested following discussions about the and appear to meet eligibility criteria, the consent form will be signed and the screening visit will be conducted. This visit will include completion of assessments to confirm inclusion and exclusion criteria. The Nurse Practitioner will complete a medical history, a physical exam, a rapid blood test for HIV, a pregnancy test for women, and collect 10ml of blood for liver function tests. Research staff will complete baseline assessments described in section 3.7 of this protocol. Those who are not eligible will receive a listing of treatment providers and encouraged to make contact for help with their substance use problems. For those who appear eligible following the screening visit, an appointment for initiating the intervention will be scheduled within 1 or 2 days.

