The mobile team's Case Management (CM) function will be performed by a master's level social worker. The CM will have primary responsibility for identifying the treatment program that best meets the needs of the participant. The CM effort will be sharply focused on identifying and removing barriers to MAT treatment engagement. This will include completing medication authorization forms and insurance enrollment if necessary, and then making referrals to additional supports, including mental health treatment, housing, medical, legal support, and peer-based recovery supports in the community. The CM will work collaboratively with participants to remove barriers to care and to enhance program outcomes and to provide psychosocial support.

The mobile team will insure that there is a clear plan for rapid engagement with ongoing treatment as soon as possible. Buprenorphine/naloxone will be provided during the time of transition to their long-term provider for up to 1 month. Telephone support will be available should participants have questions or need assistance and the mobile team will also have daily contact with participants until they complete contact with their ongoing provider.

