# 5.2 Sample Size and Power Determination

Our power analysis has been based on this primary aim. Our primary hypothesis is that participants who received rapid induction will more likely be engaged in ongoing treatment at 1- and 6-month follow-up than participants who sought treatment at BAC/CRC. We will test this hypothesis at a 5% level of significance. Our principal interest is in the comparison of engagement rates between the mobile intervention and BAC/CRC groups, at months 1 and 6. Preliminary data suggest an engagement rate of about 20-30% in the BAC/CRC group. Assuming a steady loss to attrition that yields 80% completers, and a within-subject correlation of 0.3, the methods of Diggle et al. (Diggle, Heagerty et al. 2002) show that our sample size of 125 in each group yields 80% power for differences of about 15% in engagement rates between the two groups (e.g., 80% power for BAC/CRC: 25% vs. Mobile: 40%, corresponding to a RR=1.6 and an OR=2.0)

**Propensity score model to account for non-randomized allocation:** The participants are not randomly assigned to the mobile rapid induction intervention and BAC/CRC groups, so it is possible that there will be confounding of the group effect with the effects of characteristics of the participants. We will use a propensity score approach (Rosenbaum 2002, Rothman, Greenland et al. 2008) to account for this. We will use a broad range of baseline variables as covariates in a logistic regression model predicting treatment group, including age, race/ethnicity, gender, number of previous overdoses, number of previous treatments for opiate use disorder, type of opioid used, and depression. The model will yield predicted probabilities of BAC/CRC group for all participants (the propensity score), and we will create a five-level ordinal variable based on the quintiles of the propensity score. We will then include this ordinal variable as a stratum variable in our models.

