**Analyses for the primary aim:** i.e. to evaluate the impact of the mobile, transitional MAT intervention on its ability to engage participants in targeted, existing MAT treatment slots at 1- and 6-month post-enrollment. For each of the 1- and 6-month time points, we will classify participants as being engaged/not-engaged (where non-engaged will include dropped out or missing). We will compare the groups on engagement rates at the two time points using a repeated measures logistic regression model, incorporating the propensity score as described above (Diggle, Heagerty et al. 2002). The fixed effects will be binary indicators of treatment group and time point; we will test for a group by time interaction to assess whether the group effect differs at month 1 and month 6. As there are only two time points, we will use an unstructured covariance matrix to accommodate within-participant covariance.

**Analyses for Aim 2:** We will also use a repeated measures model to compare the groups on the ASI drug composite score at months 1 and 6. The model will be similar to that described for the engagement analyses of Aim 1, but with a beta distribution assumed for the response, to accommodate the bounded range (zero to one) of the ASI composite scores. We will compare the groups on the number of overdoses per patient using repeated measures Poisson regression models, if there is sufficient variability in the number of overdoses reported. If a low rate of overdoses causes convergence issues for the Poisson model, we will classify participants as having no overdoses versus at least one, and compare the groups using repeated measures logistic regression models.

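### The month-1 engagement outcome has no rule excluding the study's own bridging buprenorphine/naloxone, so mobile-group participants still on it can be scored as engaged

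*Combined protocol and SAP*

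**What the plan says.** - **Aim.** Section 3.4 sets Aim 1 as the ability to "engage participants in targeted, existing MAT treatment slots at 1- and 6-month post-enrollment".
- **Endpoint.** Section 3.8.1: "Assessments will collect self-report of participation in MAT at the time" of assessment and over the intervening period, with confirmatory documentation from the identified provider and access to CARES service-utilization records.
- **Coding.** Under the primary-aim analyses: "For each of the 1- and 6-month time points, we will classify participants as being engaged/not-engaged", with dropouts and missing values counted as not engaged. A repeated measures logistic model compares the groups at both visits, with a test of group by time.
- **Study medication.** After the screening visit, "an appointment for initiating the intervention will be scheduled within 1 or 2 days" (Section 4.8.3). Section 4.9.1: "Buprenorphine/naloxone will be provided during the time of transition to their long-term provider for up to 1 month". The Study Summary gives the supply as four weeks.
- **First follow-up.** One month after enrollment (Section 3.4), listed as Week 4 in the compensation table (Section 10.3).
- **Vocabulary.** The introduction and Section 3.2 describe the mobile team's own induction as MAT.
- **Primary time point.** The Study Summary and Section 3.2 name 6 months alone. The hypothesis, power statement and primary analysis in Section 5.2 use months 1 and 6.

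**The concern.** The endpoint wording does not separate medication supplied by the study from treatment with an ongoing provider. At month 6 this hardly matters, because the bridging supply has long ended. At month 1 it does: a mobile participant may still be taking study drug, may truthfully report being in MAT, and may have no community provider. Read literally, the endpoint scores that person as engaged. No one in the BAC/CRC group can be scored this way, because the study gives that group no medication.

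The other safeguards do not close the gap. Provider confirmation is requested, but nothing says that the provider must be someone other than the mobile team. That team is hired by and based at Prevention Point, which also runs its own buprenorphine programme, so a confirmation from that organisation could describe either bridging or linkage. The assessors also differ by group: research assistants on the mobile team in one, TRI-PHMC assistants in the other. An unwritten coding rule would be applied by different staff who know the group.

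At stake is whether a positive primary result shows linkage to existing slots or only that the study handed out medication for a month.

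**Working it through.** **1. Timing.** Assume that enrollment is dated at the screening visit. The first dose is on day 1 or 2, and four weeks of supply add 28 days, so supply ends on day 29 or 30. Week 4 is day 28. For someone who uses the full course, the visit falls at or just before the end of supply. If enrollment is dated at induction, the two coincide. Someone who transfers earlier is off the bridge by then.

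**2. The plan's own figure.** Section 5.2 states: "We will test this hypothesis at a 5% level of significance", and "our sample size of 125 in each group yields 80% power for differences of about 15% in engagement rates between the two groups", illustrated by "80% power for BAC/CRC: 25% vs. Mobile: 40%, corresponding to a RR=1.6 and an OR=2.0". It assumes 80% completers and a within-subject correlation of 0.3. With two visits (m = 2), two-sided 5%, mean rate 0.325 and f = 1 + (m − 1)(0.3) = 1.3:

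n = [1.96·√(2·0.325·0.675·1.3) + 0.8416·√(1.3·(0.1875 + 0.24))]² / (2·0.15²) = (1.480 + 0.627)² / 0.045 = 98.7

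That is 99 completers per group, and 99/0.8 gives 124 enrolled against 125 stated. The figure reproduces, so it rests on the average of the two visits.

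**3. If bridging drug is counted.** Assume no true difference: 25% linked in both groups at both visits. Only the mobile month-1 rate x is raised, by people on study drug with no provider.

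- Contrast: d = (x − 0.25)/2.
- Variance term per group: V = p₁q₁ + p₆q₆ + 2(0.3)√(p₁q₁·p₆q₆).
- SE = √[(V_mobile + V_comparison)/(4n)].
- P(significant) = Φ(d/SE − 1.96) + Φ(−d/SE − 1.96).

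Calibration: 40% vs 25% at both visits with n = 100 gives 0.15/0.0527 = 2.85 and power 0.81, in line with the plan.

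Low end, x = 40%, n = 100: V = 0.5548 and 0.4875, SE = √(1.0423/400) = 0.0510, d = 0.075, z = 1.47, P = 0.31. High end, x = 65%: V = 0.5389, SE = 0.0507, d = 0.20, z = 3.95, P = 0.98.

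The interaction test uses x − 0.25 over √[(W_mobile + W_comparison)/n], where W is V with the covariance term subtracted. At x = 40%, n = 100, this is 0.15/0.0750 = 2.00, P = 0.52.

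| Mobile month-1 rate (assumed) | Pooled test, n = 100 | Pooled test, n = 125 | Interaction, n = 100 |
|---|---|---|---|
| 40% | 0.31 | 0.38 | 0.52 |
| 50% | 0.68 | 0.78 | 0.91 |
| 54% | 0.81 | 0.89 | 0.97 |
| 60% | 0.93 | 0.97 | 0.997 |
| 65% | 0.98 | 0.99 | >0.99 |

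The n = 125 column matters because missing is scored as not engaged, so everyone enrolled is analysed. The 54% is borrowed from the outreach programme cited in Section 2.3; it is one-month retention in methadone treatment there, not use of bridging drug, so it is only illustrative. In terms of people, the 40% to 65% range means that 15 to 40 in every 100 mobile participants are scored as engaged solely through study supply.

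**4. If bridging drug is not counted.** The inflation is absent, and month 1 measures enrollment with a provider in both groups.

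**5. If month 6 alone is primary.** For 25% vs 40%, power is 62% with 100 per group and 72% with 125. Reaching 80% needs 152 analysed per group, or 152/0.8 = 190 enrolled.

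**The case against.** The strongest reply is that the intent is clear. Aim 1 names existing slots, the hypothesis concerns ongoing treatment, Section 4.9.1 separates the bridge from the long-term provider, and Section 3.8.1 asks for provider documentation and CARES records. On that reading, all that is missing is one sentence of definition. Much of this stands, and it rules out several stronger readings that a reader might infer.

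- *Month 1 measures drug supply, not linkage.* This holds only if bridging drug is counted, which the documents neither require nor exclude.
- *Month 1 fails to compare linkage whichever way the drug is coded.* It does not fail. With bridging drug excluded, a mobile participant still in transition is truly not yet linked, and so is a BAC/CRC participant who has been referred but not enrolled. A slower early effect would then be a result, not a bias.
- *Everyone is still on study drug at Week 4.* Supply is for up to one month, with transfer intended as soon as possible.
- *Half of the primary comparison is affected.* That fits Section 5.2 but not the Study Summary or Section 3.2. Nor does the plan define the primary contrast as an equal-weight average of the two visits.
- *Excluding study drug would destroy power.* With 15% to 25% transferred by Week 4 and 40% vs 25% at month 6, power would be 0.08 to 0.31 (n = 100), but those transfer rates have no source. With 49% at month 1, the linkage figure that Section 2.3 cites for a mobile-unit programme, and 40% at month 6, it is 0.96.

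The interaction test is a real safeguard against a large month-1-only effect. It is weaker at the mild end (0.52 at a 40% rate), and the plan does not say which estimate is primary when it is significant.

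**Conclusion.** The concern holds as a gap in the definition of the primary endpoint. Read literally, the endpoint lets study-supplied medication count as engagement at month 1, in the mobile group only, although Aim 1 is about existing slots. If it is counted, a pooled two-visit test could be significant with no month-6 difference, with probability about 0.31 to 0.98 at 100 per group (0.38 to 0.99 at 125).

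Those figures rest on assumed mobile month-1 rates of 40% to 65%, 25% elsewhere, correlation 0.3, an equal-weight two-visit contrast under a normal approximation, and no propensity-stratum adjustment. They show what the missing rule could do. They do not predict how the data will be coded.

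**What to change.** In Section 3.8.1 and the primary analysis:

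1. Define engaged, at both existing time points and in both groups, as enrollment with an ongoing MAT provider other than the mobile team, confirmed by the provider or a CARES record.
2. State that study-supplied buprenorphine/naloxone does not count.
3. Report still on bridging supply at month 1 as a separate descriptive category for the mobile group.
4. Reconcile the Study Summary and Section 3.2 (month 6 alone) with Section 5.2 (months 1 and 6), and say which estimate stands if the interaction is significant.

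Keep the month-1 date. A later early reading is not needed once the definition is written, and it would move a prespecified time point.

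The first three items cost only wording and use records already being requested, with no extra visit and no change to treatment. The downside is that the mobile group's month-1 rate may look less favourable. The fourth is not free if month 6 alone is chosen: the planned 125 per group then gives 62% to 72% power for 25% vs 40%, and the power statement must be redone. All of this should be settled before outcomes are coded.

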# 3.8.2 Secondary Study Endpoints

- Evaluate the impact on the number of overdose and evaluate the change in substance use and severity of addiction using a repeated measures model to compare the groups on the ASI drug composite score at months 1 and 6.
- Cost evaluation: We will determine the economic value of the mobile intervention relative to treatment as usual from the perspective of the City of Philadelphia's Department of Public Health. [name], a Health Economist in the HIV Prevention Research Division, Department of Psychiatry, Perelman School of Medicine at the University of Pennsylvania, will lead this portion of study activities with consultations with colleagues at the Center for Health Economics of Treatment Interventions for Substance Use Disorder, HCV, and HIV (CHERISH). The results of this analysis will inform future policy decisions regarding implementation of this novel, mobile strategy for rapid initiation of MAT as a method for engagement in long-term evidence-based treatment. If the intervention in this study shows positive economic value, the City of Philadelphia's Department of Public Health may scale-up the intervention to reach more people throughout the city that may be at risk of opioid overdose. Enhanced interventions may require a greater amount of resources than alternative methods of more basic interventions or the usual standard of care. However, resource-intensive interventions may be justified through the achievement of better outcomes resulting from administering enhanced procedures.

# 4 Study Population and Duration of Participation

#### 4.1 Duration of Study Participation

The duration of study participation including screening/baseline assessments to follow-up will be 6 months.

# 4.2 Total Number of Subjects

A total of 250 participants will be engaged in the research at the time they seek treatment: 125 individuals will be enrolled as they engage with the mobile, rapid induction team and 125 individuals will be enrolled as they seek treatment from the BAC/CRC (treatment as usual).

#### 4.3 Inclusion Criteria

Participants must meet the following criteria for enrollment:

- Must be 18 years of age or older
- Opioid overdose in the prior 12 months
- Meet criteria for opioid use disorder
- Resident of Philadelphia
- Willingness and ability to participate in study procedures

# 4.4 Exclusion Criteria

- Inability to comprehend or complete study procedures
- Plans to relocate during study time frame
- Currently in medication assisted treatment (MAT) for substance use disorder
- Evidence of serious liver disease (LFTs > 3 x the upper limit of normal)
- Pregnancy or lactation
- Moderate to severe alcohol or benzodiazepine use disorder

There will be no exclusion based on gender or race/ethnicity. The participants to be recruited are expected to reflect the demographics of previous data provided by Philadelphia Department of Health on individuals who overdosed in the city of Philadelphia. Both men and women will be recruited for this study as both are affected by opioid epidemics. No gender restrictions are to be followed at recruitment. According to the available data, we are expecting enrolling about 30% of females. Minority populations will not be excluded. We are expecting enrolling about 59% European-American/non-Hispanic, 25% African-American/non-Hispanic, 15% of Hispanic/Latino, and 1% of Native American.

## 4.5 Subject Recruitment

The recruitment of participants for this study will be accomplished using a community awareness campaign involving street outreach, targeted social media, and local advertisement. This campaign will begin one month before activation of the rapid induction intervention. During this time, the mobile assessment team will begin to be present in the designated location where we will park the Mobile Clinical Trials

Unit (MCTU) – see picture.

The MCTU is a medical vehicle is built on a heavy-duty truck frame that contains an expandable waiting area and two private examination rooms. It has a sink area and a bathroom and is equipped with two locked refrigerators for specimen and medication storage. [name] serves as the Medical Director for projects and services that take place on the MCTU. The unit is approved for use by the Pennsylvania Department of Health as a site for HIV testing and the exam rooms provide comfortable and private space for counseling, interviews, and data and specimen collections.

The two neighborhoods with the highest concentrations of opioid overdose mortality will serve as our areas for engagement: Kensington and South Philadelphia. The selection of parking I ocations for the MCTU is an important process and will be informed by issues of access to the target population, data regarding recent overdoses, and community support and permissions.

For final site selection in this project, we will build on the work recently completed by the interdisciplinary "CUES Evaluation Working Group" of faculty, fellows, and stakeholders from the city and the drug-using community. The working group was funded by a grant from the Leonard Davis Institute for Health Economics (LDI) to support the development of an objective strategy for assisting the City in identifying potential locations for Comprehensive User Engagement Sites (CUES) where injections would be supervised and access to behavioral health and housing services would be provided.

Using a mixed methods approach that combines geographic analyses and qualitative research methods, the working group asked stakeholders including municipal employees, healthcare providers, PWID, and residents from across Philadelphia for their thoughts about what features would make a location either well suited or not well suited for operating a CUES. That process revealed approximately 20 aspects of the built environment or the social environment that were used to classify each city block according to the presence or absence of each type of asset, barrier, or indicator of demand. Assets for block selection included City Council District support, condom

Rapid initiation of BUP/NX Version 1: Nov-15-2018

distribution site, MAT site, HIV testing site, opioid support site, Public Health Center, pharmacy, pharmacy with Naloxone, public transit, social cohesion and syringe exchange site. Barriers to block selection included schools, daycare centers, parks and recreation facilities, police station, fire station, alcohol outlet, gentrification pressures. Factors that indicated blocks with potential demand for the service include overdose deaths, naloxone (Narcan®) administration events, police narcotics arrest, and homeless encampments. Geocoding these location features, assigning a weight to each to represent its relative importance, and summing the values into a score produced a map of Philadelphia that identified 5 specific locations that appear to be most well suited for operating a CUES. As depicted below, among these 5 locations, 1 good site is located in South Philadelphia and 1 best sites in the Kensington neighborhood.

We believe that the factors that were developed for guiding the location of the CUES also apply to locating the MCTU for this research. The circles on the map will be our preliminary target areas for exploration and finalization during the start-up phase of the research.

